Esophageal self-dilation therapy (ESDT), where the patient learns to pass a polyvinyl dilator orally on a routine basis, has been in practice since at least the 1970s, however, no prospective studies have evaluated the outcomes ESDT. The largest study to date on ESDT retrospectively studied 30 patients¹², and all the published studies on this topic consists of less than 50 patients in total¹²⁻¹⁹. In these retrospective and observational studies, ESDT appears to be effective for RBES, reducing the number of endoscopic dilations from an average of 21.7 to an average of 1¹². However, many questions with regards to ESDT remain unanswered. Firstly, in the absence of any prospective data it is uncertain how effective ESDT is. Moreover, currently patients are offered ESDT when standard therapies fail.

Hypotheses:

Among patients with refractory benign esophageal stricture who were treated endoscopically, we hypothesized the following:

- 1. Compared to an endoscopy as needed approach, esophageal self-dilation therapy decreases the number of endoscopic dilations and prolongs dysphagia free intervals
- 2. Esophageal self-dilation therapy is a safe and well tolerated therapy
- 3. ESDT significantly lowers health cost in managing refractory esophageal stricture

Primary Aims:

1. Assess the clinical efficacy of ESDT for patients with RBES defined as number of endoscopic interventions 6 months following serial dilation

Secondary Aims:

- 1. Length of intervention free interval and dysphagia score
- 2. Evaluate factors which could influence clinical success of ESDT including etiology and location of the stricture
- 3. Assess the safety of ESDT by identifying clinically significant adverse events including perforation, bleeding and pain.
- 4. Assess acceptance of ESDT by measuring the number of patients who accepts the procedure and are able to complete it over the total number of patients offered ESDT
- 5. The cost saving in ESDT compared to the current standard of care (repetitive endoscopic dilation)
- 6. Evaluate long term outcomes of self-dilatation at 3, 6, 9 and 12 months following participation in the 6 month randomized or prospective observational trial

Methods:

Study Design:

This is a prospective randomized controlled trial evaluating the outcomes of self-dilation. Patients who present to the esophageal clinic in Rochester MN and Mayo Clinic Phoenix, AZ with refractory benign esophageal strictures who undergo standard clinical care of serial endoscopic dilation to achieve an esophageal diameter of at least 10-12 mm will be randomized to either continuing standard clinical care consisting of endoscopic dilation as needed vs self-dilation therapy.

Inclusion Criteria for Patients:

- 1. 18 years of age or older
- 2. Refractory benign esophageal stricture defined as an esophageal stricture with persistent dysphagia despite undergoing 5 endoscopic dilations within a 1 year period. Persistent dysphagia will be considered if patients has solid food dysphagia at least once a week

Exclusion Criteria

- 1. Patient with malignant esophageal stricture
- 2. Angulated stricture which prevents safe passage of Maloney dilator in office setting
- 3. In ability to achieve an esophageal diameter of 10 mm with endosocpic dilatiation
- 4. Known significant esophageal motor disorder (i.e. achalasia, aperistalsis, functional obstruction, jackhammer, distal esophageal spasm)*

- 5. The presence of esophageal stent
- 6. Inability to learn self-dilation secondary to blindness or cognitive dysfunction
- 7. Use of chronic anticoagulants

Study Flow and Recruitment

- 1. Patients referred to the esophageal clinic with dysphagia secondary to RBES will be asked to complete the Mayo Dysphagia Questionnaire (MDQ-30). The MDQ will be completed before obtaining informed consent. Quality of life will also be measured at the beginning at end of the 6 months using Short form-36
- 2. First, patients will undergo the standard of care which is serial endoscopic therapy with esophageal dilation. Patients will be dilated 1-3 times a week with the aim to achieve a post-dilation luminal diameter of at least 10-12 mm
- 3. After informed consent, participants will be randomized to one of two groups using a block randomization approach; Group 1) self-dilation, group 2) observation with repeat endoscopy and dilations as needed at symptoms recurrence.
- 4. Patients randomized to self-dilation who refuse self-dilation will be assigned to the observation group and will be counted in the ESDT failure
- 5. Patients randomized to ESDT will be taught ESDT immediately following the last endoscopic dilation. ESDT teaching will take over 1-3 training sessions by one of two esophageal physicians and a nurse. Patients will be instructed to start ESDT twice a day. If dysphagia is adequately controlled, and there was no resistance with passing the dilator, patients will be asked to decrease the frequency of ESDT to daily, weekly, and monthly over an average period of 6 months as directed by the esophageal care team.
- 6. Patients randomized to the observation group will undergo repeat endoscopy and dilation as needed if their dysphagia relapse which is the current standard of care. A relapse will be considered if a patient developed solid food dysphagia at least once a week.
- 7. Patients in the observation group who requires 2 endoscopic dilation within 3 months will be offered to cross over to the self dilation group
- 8. Patients in the self dilation group who can not tolerate self dilation but require more treatment will be offered to crossover to the standard clinical care grouph endoscopic dilation as needed after 3 months from the entry point
- 9. At the end of the six months, the standard clinical care group will be offered self-dilation.
- 10. At any point of the study if patients decide to crossover to the other group, this will be allowed but counted as treatment failure
- 11. Close supervision and follow up will be performed via weekly phone calls from a member of the study personnellPatients will be asked to complete the MDQ-30 monthly and at the end of the study.
- 12. Patients who decline participation in the randomized study will be offered both treatments clinically then will be followed prospectively and their data will be collected. These patients will be asked to fill the dysphagia score to assess symptoms regardless of the method of treatment.
- 13. At the conclusion of the 6 months randomized or observational study duration patients will be offered the following:
 - 1. All patients who participated in the randomized or observational study will be offered to continue prospective follow up with phone calls to obtain the MDQ-30 score and

need for endoscopy at 3, 6, 9, and 12 months after conclusion of the initial 6 month duration of the study

Remuneration:

- 1. Patients in the randomized self-dilation group will be provided with the self-dilator free of charge.
- 2. Patients in the randomized observation group will receive endoscopic dilation as needed with charges to the patients and their health insurance as appropriate since this is the standard of care
- 3. Patients in both groups will receive stipend of \$25 for each questionnaire for the time spent in completing the dysphagia questionnaire during the randomized 6 month study duration
- 4. Patients who participate in the prospective observational study, and who either chose self-dilation or observation will receive stipend of \$25 for each questionnaire for the time spent in completing the dysphagia questionnaire

Patients who agree to the prospective extension study will receive a stipend of \$25 for each of the 4 monthly MDQ phone calls to collect questionnaires.

Statistical Analysis:

Sample Size Estimation:

Based on the current knowledge from our prior experience, the clinical success of ESDT appears to be 80%. The clinical success of repetitive endoscopic dilation is reported in the literature to be 30%. Assuming a 50% improvement in clinical success with ESDT and using 1:1 randomizing, the estimated minimum number of patients needed is 30 patients (15 in each group). Given the extreme paucity of data on self dilation and ambiguity about the potential improvement we intend to recruit 40 patients across the two sites (Rochester and Phoenix). This estimated number will provide at least 80% power of finding a significant difference at a P value of 0.05

Up to 40 patients who chose not to participate in the randomized trial, but who agree to be followed in the prospective observational group will be recruited.

The following table summarizes the key questions and corresponding approaches to be addressed by this study.

Primary Endpoint:

1. Compare the number of endoscopies required in a 6 month interval in patients who achieved at least a 10-12 mm esophageal diameter during serial dilation for RBES and were subsequently treated with ESDT versus standard clinical care.

Secondary Endpoints:

- 1. Determine the length of intervention free interval
- 2. Dysphagia score
- 3. Number of clinically significant adverse events including perforation, bleeding and pain
- 4. Cost of ESDT compared to the current standard of care (repetitive endoscopic dilation)

Definition:

Perforation will be defined as Evidence of air or luminal contents outside the GI tract. Bleeding will be defined as hematemesis and/or melena or hemoglobin drop >2 g/L

Question	Approach	Statistical Test
Clinical success	Compare the number of	Logistic regression in a
	patients who remained free	univariate and multivariate
	of endoscopic therapy	analysis
	between the two groups	
Time to the next endoscopy	Compare time endoscopic	Cox regression and Kaplan
	therapy. Patients who	Meier
	requires endoscopic dilation	
	will be considered failure	
Adverse events	Compare the number of	Logistic regression in a
	patients who developed	univariate and multivariate
	adverse events between the	analysis
	two groups	
The cost	Compare the cost of	Linear regression
	treatment including	
	endoscopic therapy,	
	hospitalization from	
	complications	
Factors affecting clinical	Investigating factors which	Multivariate logistic regression
success in ESDT	could determine clinical	
	success including age,	
	gender, etiology, length of	
	the stricture and location of	
	the stricture	

References:

- 1. Spechler SJ. American gastroenterological association medical position statement on treatment of patients with dysphagia caused by benign disorders of the distal esophagus. Gastroenterology 1999;117:229-33.
- 3. de Wijkerslooth LR, Vleggaar FP, Siersema PD. Endoscopic management of difficult or recurrent esophageal strictures. Am J Gastroenterol 2011;106:2080-91; quiz 2092.
- 6. Ramage JI, Jr., Rumalla A, Baron TH, et al. A prospective, randomized, double-blind, placebo-controlled trial of endoscopic steroid injection therapy for recalcitrant esophageal peptic strictures. Am J Gastroenterol 2005;100:2419-25.

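### No planned analysis names the prior dilation count as a covariate, and none models the 6-month endoscopy count itself: a cheap, optional improvement

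*Combined protocol and SAP*

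**What the plan says.** Under Primary Endpoint, item 1, the outcome is a count: "Compare the number of endoscopies required in a 6 month interval". Under Inclusion Criteria for Patients, item 2, a refractory stricture is one with persistent dysphagia "despite undergoing 5 endoscopic dilations within a 1 year period". Staff must therefore look at each patient's dilation history before enrolment.

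The table of questions and tests that closes the Statistical Analysis section has five rows:

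- Clinical success, taken as remaining free of endoscopic therapy: univariate and multivariate logistic regression, no covariates listed.
- Time to the next endoscopy: Cox regression and Kaplan-Meier, no covariates mentioned.
- Adverse events: univariate and multivariate logistic regression, no covariates listed.
- Cost: linear regression, no covariates mentioned.
- Factors affecting success in ESDT: multivariate logistic regression on factors that include age, "gender, etiology, length of" the stricture, and its location.

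Prior dilations appear in none of them, and no row analyses the number of endoscopies as a number. Study Flow and Recruitment, item 3, describes blocked randomisation and names no stratification factor.

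**The concern.** For a count outcome, the same kind of count before entry is usually among the first covariates to consider. Five dilations is a floor. The background section cites a retrospective series that averaged 21.7 dilations before ESDT, over a period it does not state. If patients enter with very different dilation rates, part of the noise in the 6-month count comes from differences that could have been measured beforehand. With 20 per arm and no stratification, the arms may also differ in prior rate by chance, and that would shift the estimate.

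At stake are some precision and protection against a chance imbalance in a trial of 40. There is also a question of pre-specification: the two between-group multivariate models leave their covariates open, so the choice could be made after the data are seen.

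**Working it through.** **1. The plan's own figure.** Sample Size Estimation says that "the clinical success of ESDT appears to be 80" per cent and that "The clinical success of repetitive endoscopic dilation is reported in the literature to be 30" per cent, with 1:1 allocation, P = 0.05 and 80% power. The two-sided test of two proportions with pooled variance (mean proportion 0.55) gives

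n per arm = [1.96 × √(2 × 0.55 × 0.45) + 0.842 × √(0.8 × 0.2 + 0.3 × 0.7)]² / 0.5² = (1.379 + 0.512)² / 0.25 = 14.3, rounded up to 15.

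This matches the stated minimum of 30. Power is 82.0% at 15 per arm and 92.1% at 20 (Fisher's exact test: 68.0% and 84.6%). With 40 patients the claim of at least 80% power holds without any covariate, but for a yes/no outcome and not for the count.

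**2. What a baseline covariate can give in general.** In a linear analysis the variance is multiplied by (1 − ρ²), where ρ is the correlation of baseline with outcome. One covariate costs a factor of about 37/36 at N = 40. The equivalent unadjusted N is 40 / [(1 − ρ²) × 37/36]:

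| ρ | Equivalent N | Power, if 80% unadjusted |
|---|---|---|
| 0.1 | 39.3 | 79.3% |
| 0.2 | 40.5 | 80.5% |
| 0.3 | 42.8 | 82.6% |
| 0.5 | 51.9 | 89.1% |
| 0.6 | 60.8 | 93.2% |

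Break-even is at ρ² = 1/37, so ρ is about 0.16. The documents do not give ρ. An assumed gamma-Poisson model (mean 6 to 12 dilations a year, at least 5 required, full carry-over, no treatment effect) gave ρ from 0.36 to 0.86. That is illustrative only, and ρ would probably be lower in an ESDT arm with few endoscopies.

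**3. The gain at the plan's own effect.** If success means endoscopy-free, as the table has it, the implied hazard ratio is ln 0.8 / ln 0.3 = 0.223 / 1.204 = 0.19. With a constant common rate, the expected endoscopies are 20 × 1.204 = 24.1 in control and 20 × 0.223 = 4.5 in ESDT. The Poisson part of the variance of the log rate ratio is then about 1/24.1 + 1/4.5 = 0.26. A baseline covariate cannot remove that part.

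Two separate gamma-Poisson simulations were calibrated to 30% and 80% endoscopy-free, with 20 per arm and the prior rate carrying over. In the first (800 runs per setting, patient noise SD 0.4 on the log scale), power without and with the log prior count was:

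| Between-patient CV | Count model | Cox model |
|---|---|---|
| 0.4 | 96%, 95% | 92%, 92% |
| 0.6 | 95%, 96% | 91%, 92% |
| 0.9 | 96%, 98% | 92%, 93% |

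The variance of the log rate ratio ranged from 1% higher to 6% lower. The second simulation (500 runs per setting) gave about 97% count-model power either way and a variance change of −3% to +1%.

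**4. The gain at a weaker effect.** With the planned control rate and a rate ratio of 0.5, the first simulation gave count-model gains of 1, 5 and 9 points of power at CV 0.4, 0.6 and 0.9. The second gave −2 to +13 points with full carry-over and about 0 with half. Simulation error on one power estimate is up to √(0.25/500) = 2.2 points, so the −2 is not a demonstrated loss. Rejection under no effect stayed at 3-6%.

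**5. Chance imbalance.** Assuming a mean of 8 dilations a year, at least 5 required and 20 per arm, the arms' mean prior counts differed by a ratio above 1.2 in about 14-17% of simulated trials at CV 0.4, 23-25% at CV 0.6 and 33-37% at CV 0.9.

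**The case against.** The strongest case on the other side is that nothing is wrong with the plan. An unadjusted comparison of randomised groups is valid, and at the effect the sponsor expects the covariate changes almost nothing. That stands, and it sets the priority of the point.

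Carry-over is also doubtful. Everyone is first dilated to at least 10-12 mm. Observation patients who need 2 dilations within 3 months are offered crossover, which may cut short the counts of those with the highest rates. The simulations do not model this. It stands too, and is why the lower end of the gain is nil.

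Three stronger readings are tempting, and the documents do not support them.

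- A reader might infer that the plan excludes the prior count. It does not: the multivariate rows leave covariates open, and the factor list for ESDT is worded as non-exhaustive. The count is unnamed, not ruled out.
- A reader might infer that the value is already in hand. Criterion 2 is a threshold within some 1-year period. It does not fix that period as the year before entry or require an exact count. The serial dilations before randomisation blur the window further.
- A reader might infer a large loss of power. Gains of 8 to 16 points do appear in simulation, for example 58% to 66% or 66% to 82%. Those runs assume a mean of 8 dilations a year and a rate ratio of 0.5. If that prior rate carries over unscaled, only about 5% of controls stay endoscopy-free, against the planned 30%. The 21.7 average has no stated period, so it does not show the spread of yearly rates in this population.

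**Conclusion.** The point holds as an optional, inexpensive improvement. No row names the prior dilation count, and the more basic gap is that no row models the primary count. Adding both would have a negligible effect on power at 30% against 80% success. At a rate ratio of 0.5 with the planned control rate, the gain is from about nil to roughly 10 points. That range rests on assumed between-patient variation (CV 0.4 to 0.9) and assumed carry-over. The sample size section itself speaks of ambiguity about the likely improvement, so the weaker effect is worth covering. In the Cox and logistic models any gain comes mainly from the adjusted estimate moving away from the null and not from a smaller standard error. The possible loss is slight: under one point of power at ρ = 0.1 in the linear approximation.

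**What to change.** - Record for every randomised patient the exact number of dilations in the 12 months before referral, excluding the study's serial dilations.
- Add a row to the analysis table with a count model for the 6-month endoscopies, for example quasi-Poisson or negative binomial.
- Pre-specify the logarithm of the prior count as the single covariate in that model and in the Cox model for time to next endoscopy.
- Report the unadjusted result beside each adjusted one.

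The cost is a few lines of SAP text, one data field, one degree of freedom, and outside records for some referred patients. It needs no extra patients and no change to care.

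### The plan does not say in which arm the endoscopies of ESDT refusers and crossovers are counted, or whether refusal and elective crossover are part of clinical success

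*Combined protocol and SAP*

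**What the plan says.** The Study Design paragraph describes a randomised comparison: patients "will be randomized to either continuing standard clinical care" or self-dilation. The Primary Endpoint compares the number of endoscopies over 6 months in patients who reached the target diameter and "were subsequently treated with ESDT versus standard clinical care".

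Study Flow and Recruitment then provides for patients who leave their allocated treatment:

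- Item 4: "Patients randomized to self-dilation who refuse self-dilation will be assigned to the observation group and will be counted in the ESDT failure".
- Item 7: "Patients in the observation group who requires 2 endoscopic dilation within 3 months will be offered to cross over to the self dilation group".
- Item 10: "At any point of the study if patients decide to crossover to the other group, this will be allowed but counted as treatment failure". This covers switching in either direction.

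In the table of questions and tests, the clinical success row counts "patients who remained free" of endoscopic therapy in the two groups, by logistic regression. The time-to-endoscopy row treats only a need for endoscopic dilation as failure. Neither row mentions refusal or crossover.

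The combined protocol and SAP names no intention-to-treat, as-treated or per-protocol set.

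**The concern.** Two things are left open, and they differ in weight.

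The first concerns the primary count. Item 4 places refusers in observation but charges them to ESDT as failures. That works for a yes/no outcome. A number of endoscopies has no failure value, so item 4 does not say what a refuser contributes to the count, or to which arm. The endpoint's 'treated with' wording leans towards treatment received. If refusers' endoscopies are counted in observation, patients move between arms after randomisation for reasons that may be related to prognosis.

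The second concerns the binary outcome. The table scores success by endoscopy alone, whereas items 4 and 10 score refusal and elective crossover as failure. An endoscopy-free patient who refuses or switches is a success under one rule and a failure under the other.

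Refusal and switching are foreseen by the plan itself, and acceptance of ESDT is a secondary aim. With about 20 patients per arm, the coding of a few can decide the result, and nothing stops the rule from being chosen after the data are seen.

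**Working it through.** **The plan's own figure.** Sample Size Estimation takes 80% success for ESDT, and for standard care says "The clinical success of repetitive endoscopic dilation is reported in the literature to be 30" per cent. With two-sided 0.05 (sidedness is not stated), 80% power and pooled variance:

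n = [1.960·√(2·0.55·0.45) + 0.842·√(0.80·0.20 + 0.30·0.70)]² / 0.50² = (1.379 + 0.512)² / 0.25 = 14.3, so 15 per arm.

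This is the stated 30 patients. At the intended 40 (20 per arm), power is 92.1% by this approximation and 88.9% by exact enumeration of the Wald logistic test. The sample size is not in dispute, but it assumes no refusal and no crossover.

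**How each type of patient is handled**

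| Patient | Table, clinical success | Items 4 and 10 | Arm for endoscopy count |
|---|---|---|---|
| ESDT refuser, endoscopy-free | success | ESDT failure | not stated |
| ESDT refuser with an endoscopy | failure | ESDT failure | not stated |
| Elective crossover, endoscopy-free | success | failure | not stated |
| Item 7 crossover (already 2 dilations) | failure | failure if item 10 applies | not stated for later endoscopies |

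The two success definitions differ only in rows 1 and 3. The arm for the count is open in every row.

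**Primary count, no treatment effect.** Assumptions, none of them in the documents: 4 of 20 in each arm are of the kind who would refuse ESDT; their endoscopy rate is twice or half that of the others (mean m); the test is a two-sided rank-sum.

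- By randomised arm, refusers at 2m: both arms average (16m + 4·2m)/20 = 1.20m. There is no bias.
- Refusers' counts moved to observation, refusers at 2m: ESDT averages m over 16 patients; observation averages (16m + 4·2m + 4·2m)/24 = 1.33m. The spurious ratio is 0.75.
- Moved, refusers at m/2: ESDT averages m; observation averages (16m + 4·0.5m + 4·0.5m)/24 = 0.83m. The spurious ratio is 1.20.

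Simulation used Poisson counts and counts with gamma frailty of variance 1, with means matched to 30% endoscopy-free (1.204 and 2.333). By randomised arm, about 2-3% of trials are significant in each direction. With counts moved, about 6-12% favour ESDT when refusers need twice as many endoscopies, and about 6-8% go against ESDT when they need half as many.

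**Binary row, planned effect.** Let r be the proportion of the ESDT arm who refuse, and assume refusers are endoscopy-free at the control rate of 30%. ESDT success is 0.80(1 − r) + 0.30r by the table and 0.80(1 − r) by item 4. Power is against 30%, 20 per arm, exact Wald:

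| r | Table | Power | Item 4 | Power |
|---|---|---|---|---|
| 0 | 0.80 | 89% | 0.80 | 89% |
| 0.10 | 0.75 | 81% | 0.72 | 75% |
| 0.20 | 0.70 | 70% | 0.64 | 55% |

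In whole patients, 16/20 against 6/20 gives Fisher p = 0.0036. Recoding three endoscopy-free ESDT patients as failures gives 13/20 against 6/20, p = 0.056.

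**Item 10 coding, no effect, 30% success in both arms.** If a proportion c of endoscopy-free patients switch, success in that arm becomes 0.30(1 − c), that is 0.27, 0.24 or 0.21 for c = 10%, 20% or 30%. The chance of a significant result favouring ESDT is 2.1% with no switching.

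| c | Controls only switch | Equal switching in both arms |
|---|---|---|
| 10% | 3.3% | 1.9% |
| 20% | 5.0% | 1.7% |
| 30% | 7.3% | 1.3% |

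By symmetry, switching only out of ESDT gives 3.3% to 7.3% against ESDT.

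**The case against.** The best defence is that items 4 and 10 are specific rules added to a general endpoint, so that success means endoscopy-free with no refusal and no elective crossover. That composite is coherent. A reader might infer that the table and these items flatly contradict each other; the text does not support that. What is missing is the sentence that joins them.

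A reader might also infer that item 4 leaves refusers without an arm altogether. For the binary row it does not: it charges them to ESDT. The gap is in the count and in the other table rows (time to endoscopy, adverse events, cost).

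Nor do the documents show that item 10 favours ESDT. It applies in both directions, and equal switching produces no inflation. Inflation needs asymmetric switching, for which the plan gives no evidence. Larger figures would follow from a higher common success rate, but 30% is the only standard-care rate given.

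The plan does address refusal in part: randomisation follows consent, those who decline the trial enter an observational cohort, and acceptance and completion of ESDT are a secondary aim. Item 8, on ESDT patients who cannot tolerate the treatment, shows no specific conflict of its own.

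All of this narrows the second issue. None of it supplies an analysis set, or an arm for the endoscopies of refusers and crossovers.

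**Conclusion.** The concern holds in two parts. The more serious is that the primary count has no analysis set, while its wording and item 4's reassignment permit a comparison by treatment received. They do not prescribe one, so it would go too far to say that the plan specifies an as-treated analysis. Under the assumed 20% refusal and twofold prognostic difference, that reading raises one-directional error from about 2-3% to about 6-12% or 6-8%, in a direction set by the refusers' prognosis.

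The lesser part is that the plan does not say whether items 4 and 10 belong to clinical success. This matters only for patients who refuse or cross over while endoscopy-free, but at 10-20% refusal it moves power by 6 to 15 points (81% against 75%; 70% against 55%). Any false-positive inflation from item 10 depends on asymmetric switching.

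Refusal and switching rates, refusers' prognosis and the rank-sum test are all assumptions. The textual gaps do not depend on them.

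**What to change.** - State that all efficacy endpoints are analysed by randomised arm over the full 6 months, with refusers and crossovers kept in their arm with their actual endoscopy counts. In the primary endpoint, replace 'treated with' by 'randomised to'.
- State before analysis whether items 4 and 10 are part of clinical success. Report the other definition (endoscopy-free only, or endoscopy-free with no refusal or elective crossover) as a sensitivity analysis.
- Report refusals and crossovers by arm, with the reason and whether the patient had relapsed at the switch. Item 6 supplies the criterion: "A relapse will be considered if a patient developed solid food dysphagia at least once a week".
- Reconcile items 4 and 10 with the endpoint definitions. No change to the clinical crossover rules is proposed.

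The cost is SAP wording, one sensitivity analysis and two recorded items per switch. There are two statistical downsides.

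First, refusal dilutes the by-arm count. With refusers at the control rate, simulated rank-sum power at the planned effect is about 96-97% with no refusals, 90-92% at 10% and 78-83% at 20%.

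Second, endoscopy-free-only scoring can count a relapsed control who takes ESDT in place of endoscopy as a success. If a proportion q of relapsing controls do so and 80% of them then stay endoscopy-free (assumptions), control success is 0.30 + 0.70·q·0.80 = 0.356, 0.412 or 0.468 for q = 10%, 20% or 30%. Power then falls from 89% to 80%, 69% or 56%. This is why both codings should be reported.

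### The only primary endpoint is a count of endoscopies over 6 months, but no planned analysis compares that count, and the stated 80% power belongs to a binary outcome in neither endpoint list

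*Combined protocol and SAP*

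**What the plan says.** All places are in the combined protocol and SAP.

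- **Primary Aims:** efficacy is defined as the "number of endoscopic interventions 6 months following serial dilation".
- **Primary Endpoint:** one item, "Compare the number of endoscopies required in a 6 month interval", ESDT versus standard clinical care.
- **Secondary Endpoints:** intervention-free interval, dysphagia score, adverse events and cost. Clinical success is not among them.
- **Sample Size Estimation:** "the clinical success of ESDT appears to be 80" per cent, against 30% for repeated endoscopic dilation. This gives 30 patients at 1:1. Because of "ambiguity about the potential improvement" the target is raised to 40, and "This estimated number will provide at least 80% power of finding a significant difference" at a P value of 0.05.
- **Table of questions and tests**, introduced by "The following table summarizes the key questions and corresponding approaches": five rows. Clinical success compares "patients who remained free" of endoscopic therapy, by logistic regression. Time to next endoscopy uses Cox regression and Kaplan-Meier. The other rows are adverse events, cost, and factors affecting success.
- **Study Flow and Recruitment:** item 4 counts patients who refuse self-dilation as ESDT failures. Item 7 offers crossover to observation patients who need 2 dilations within 3 months. Item 10 counts any elective crossover as treatment failure.

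**The concern.** The aim and the endpoint are a number per patient. The two efficacy rows of the table use only whether a first endoscopy occurred and when. A patient with one endoscopy and a patient with five are the same in the logistic row, and the Cox row stops at the first event. Yet item 7 expects observation patients with repeat dilations, and Hypothesis 1 is that ESDT reduces the number of dilations.

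Followed as written, the plan produces no estimate or p-value for the count it calls primary. Someone would have to choose the test later, possibly with the data in view. A reader would also take the stated 80% power to refer to the primary endpoint, which it does not.

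**Working it through.** **1. Reproduce the plan's figure.** Inputs from Sample Size Estimation: p1 = 0.80, p2 = 0.30, alpha 0.05 (taken as two-sided, since sidedness is not stated), power 0.80, 1:1. The mean proportion is 0.55.

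n per arm = [1.96 × √(2 × 0.55 × 0.45) + 0.842 × √(0.80 × 0.20 + 0.30 × 0.70)]² / (0.80 − 0.30)²
= (1.379 + 0.512)² / 0.25 = 14.3, rounded up to 15, so 30 in total.

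The plan's number is therefore a comparison of two proportions. Recruiting 40 at 1:1 gives 20 per arm, where exact power for 80% versus 30% is 88.9% (logistic, Wald), 90.8% (logistic, likelihood-ratio) or 84.6% (Fisher). The claim of at least 80% is correct for the binary outcome.

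**2. Look for count inputs.** The documents give no 6-month mean per arm, no rate ratio and no dispersion. The only mean counts are in the background, "reducing the number of endoscopic dilations from an average of 21.7" to an average of 1. That is a retrospective before-and-after figure with no stated observation period. Power for the count cannot be derived from the documents and can only be shown over assumptions.

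**3. Power for the count under assumptions.** Counts are Poisson or negative binomial with variance m + k·m², k = 0, 0.5 or 1. There are 20 per arm and a two-sided 5% rank test. Means are set so that the probability of zero endoscopies equals the assumed endoscopy-free share. For Poisson, m = −ln(0.30) = 1.20 in observation and −ln(0.80) = 0.22 in ESDT. For k = 1, m = 1/0.30 − 1 = 2.33 and 1/0.80 − 1 = 0.25. Rank-test figures are from 40,000 simulated trials per scenario; logistic figures are exact.

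| Endoscopy-free shares | Rank test on count (k = 0 / 0.5 / 1) | Logistic (Wald / LR) | Tests disagree |
|---|---|---|---|
| 80% vs 30% | 95.6 / 96.5 / 97.1% | 88.9 / 90.8% | 5–8% of trials |
| 60% vs 30% | 60.9 / 65.4 / 69.7% | 44.6 / 46.3% | 17–26% of trials |
| 30% vs 30% | 4.7 / 5.0 / 4.7% | 4.1 / 5.3% | – |

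If the count effect is instead set as a rate ratio, with control means of 1.2 to 3 and k from 0 to 1, rank-test power is about 53–99% for a ratio of 0.3 and about 24–86% for 0.5.

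With no effect, taking whichever of the rank and logistic tests is significant gives about 7–8% false positives.

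**4. What the zero split discards.** In the 30% observation scenario with Poisson counts, P(1) = 0.30 × 1.204 = 0.361. The share with two or more among those with any is then (0.70 − 0.361)/0.70 = 48%. With k = 0.5 and k = 1 it is 61% and 70%.

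**5. Whether the failure rules change clinical success.** The table defines it as free of endoscopic therapy. Items 4 and 10 use the terms ESDT failure and treatment failure, and the documents do not say whether these override the table. Suppose they do, and remove an assumed 10% or 20% of successes:

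| Affected | Success rates | Logistic power (Wald / LR) |
|---|---|---|
| ESDT arm only, 10% | 0.80 × 0.9 = 72% vs 30% | 75.0 / 76.0% |
| ESDT arm only, 20% | 0.80 × 0.8 = 64% vs 30% | 55.0 / 56.4% |
| Both arms, 10% | 72% vs 0.30 × 0.9 = 27% | 81.2 / 82.1% |
| Both arms, 20% | 64% vs 0.30 × 0.8 = 24% | 70.8 / 72.8% |

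**The case against.** The fairest reply is that the clinical success row is the primary endpoint in reduced form. Endoscopy-free status is the zero versus one-or-more split of the same count, Secondary Aim 2 already uses the term, and the sample size fits it. On this reading the plan does name an efficacy test with matching power, and only the labels are out of line. Part of this stands: the outcomes are closely related, the table does give a working definition, and the sample-size arithmetic is sound. But the split is a different quantity from the number of endoscopies, and nothing in the plan says that it stands in for the primary endpoint.

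A reader might go further and infer that the trial is underpowered for its primary endpoint. The documents do not support that. They give no planned effect for the count, and if the endoscopy-free shares really are 80% and 30%, the assumed models put the rank test above 95%. The opposite inference, that power for the count is assured, fails for the same reason: it depends on the assumed link between zero shares and means, and the rate-ratio scenarios go well below 80%.

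A reader might also infer that the failure rules necessarily take the binary analysis below 80%. That too depends on an unsourced loss of successes and on which arm bears it. With a 10% loss in both arms, power stays above 80%.

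**Conclusion.** The point holds from the text alone. The only primary endpoint is a count, none of the five table rows compares it, and the power statement is for a binary outcome in neither endpoint list. This is a fault of alignment and pre-specification and should be corrected before any data are seen.

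Its size depends on the true effect. Near the planned 80% versus 30%, the choice of test seldom changes the conclusion. At a smaller effect such as 60% versus 30%, which the plan's own caution about the improvement makes relevant, the choice changes significance in roughly one trial in six to one in four. The false-positive inflation from choosing between the two tests is modest. All count figures rest on the assumed distributions, and the failure-rule figures on assumed losses of 10% and 20%.

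**What to change.** Make the primary endpoint, its test and the power statement refer to one outcome, in one of two ways.

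- **(a) Keep the count as primary.** Add a table row for the number of endoscopies in the 6 months after randomisation, compared by randomised arm, with endoscopies counted to 6 months in everyone, including after refusal or crossover. Name one governing test that holds its level with 40 patients, for example a permutation or rank test, and report the rate ratio as descriptive only. State that the 80% power refers to clinical success, and give power for the count over a stated range of means and dispersion.
- **(b) Make endoscopy-free status at 6 months primary.** The existing sample size and logistic row already fit it. Change the primary aim and endpoint to match, and list the count as a secondary endpoint with a named test so that repeat endoscopies are still compared.

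Under either option, list clinical success as an endpoint and state whether refusal or crossover counts as failure in it.

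The cost is wording, one extra analysis and no extra patients. Endoscopies must be recorded to 6 months in all randomised patients; the weekly calls in Study Flow and Recruitment, item 11, could collect this.
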